12.5.2.1 Primary Analysis

Change in ALP at each scheduled timepoint up to Week 24 will be explored via tabulation and graphs for the FAS. Counts for the number of subjects that have a ≥15%, ≥30%, ≥40%, ≥50% and ≥70% reductions in ALP from baseline will be presented (these counts will be cumulative i.e a subject with ≥30% reduction at Week 24 will be counted in both ≥15% and ≥30% categories. Summary statistics for each schedule timepoints will be presented. These will include the geometric mean, geometric mean +/- geometric

Version Date: 27-June-2024

Sponsor: Calliditas Therapeutics Suisse SA

Protocol No: GSN000350

standard deviation, median, minimum, maximum. Baseline will be summarized in two ways – including all baseline data and baseline recalculated for subjects with evaluable Week 24 results (i.e. the subset of patients who have both baseline and week 24 ALP results).

In order to summarize % change at each scheduled timepoint, the ratio of ALP to baseline will be calculate for each scheduled timepoint and a logarithmic transformation applied. The mean and mean +/- standard deviation and mean +/- standard error of the log ratios will be calculated. The results will be backtransformed to get the geometric mean ratio (+/- geometric standard deviation and +/- geometric SE).

These results will be converted to the % scale and plotted as a line graph for each treatment group. ALP values after initiation of PBC-related medication will be treated as missing values at the analysis visit following initiation of the medication.

For the primary analysis, the ratio of ALP at week 24 to baseline will be log-transformed, as will ALP data from other timepoints used in the model. This will be analyzed using a Mixed Model Repeated Measures (MMRM) analysis based on the FAS and incorporating ALP data from baseline, weeks 2,4,8,12 and 24. Baseline ALP will be included as a covariate and will be calculated as the geometric mean of prerandomization ALP results, as defined in section 10.1 and log-transformed prior to inclusion in the analysis model. The model will also include terms for treatment group, visit, log(baseline) by visit, and visit by treatment group interaction. Subject will be included as a random effect.

the Mixed Model Repeated Measures (MMRM) model can be mathematically represented as follows:

$$Y_{ij} = \beta_0 + \beta_1$$

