 · Treatment $_i + \beta_2$ · Visit $_j + \beta_3$ · (log (Baseline ALP $_{ij}$)) + β_4 · (log (Baseline ALP $_{ij}$ × Visit $_i$) + β_5 (Treatment $_i$ × Visit $_i$) + b_i + ϵ_{ij}

- Y_{ii} is the observed response (log-transformed ratio of ALP at visit j (up to Week 24) to baseline).
- β_0 is the overall intercept.
- β_1 is the effect of treatment group *i*.
- β_2 is the effect of visit j.
- β_3 is the effect of baseline ALP.
- β_4 is the interaction between log-transformed baseline and visit.
- β_5 is the interaction between treatment and visit.
- b_{ijk} represents the random effect for the subject k.
- ϵ_{ii} is the residual error term.

An unstructured covariance matrix will be used to model the within-subject correlation of data. The Kenward-Roger's degrees-of-freedom adjustment will be used. Restricted maximum likelihood will be used to obtain parameter estimates.

Assessment of model assumptions:

Model assumptions of the MMRM will be assessed. Where the residual errors ϵ_{ij} are assumed to be independent and identically distributed with constant variance; the random effects b_{ijk} are assumed to be normally distributed with mean zero.

- 1. The assumption of linearity (linear relationship between log-transformed ratio of ALP with independent variables) and homoscedasticity will be checked using residual plots.
- 2. The assumption for normality of residuals will be checked using QQ plots.

Assessment of model convergence:

Version Date: 27-June-2024

Sponsor: Calliditas Therapeutics Suisse SA

Protocol No: GSN000350

- If the model using unstructured covariance matrix does not converge, heterogeneous Toeplitz covariance structure will be used instead of the unstructured covariance matrix. If the model still fails to converge, the Toeplitz structure will be used.
- If the above method does not lead to convergence of the model, consideration will be given to increasing the maximum number of iterations, changing the optimization technique, or adjusting the convergence criteria to promote model convergence.
- If the above optimization still fails to make the model converge, the following models (removing baseline * visit interaction term and removing the baseline term) will be used until the model converges.

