$$Y_{ij} = \beta_0 + \beta_1 \cdot \text{ Treatment }_i + \beta_2 \cdot \text{ Visit }_j + \beta_3 \cdot \left(\log\left(\text{ Baseline ALP }_{ij}\right)\right) + \beta_4\left(\text{ Treatment }_i \times \text{ Visit }_j\right) + b_i + \epsilon_{ij}$$

$$Y_{ij} = \beta_0 + \beta_1 \cdot \text{ Treatment }_i + \beta_2 \cdot \text{ Visit }_j + \beta_3 \cdot \left(\text{ Treatment }_i \times \text{ Visit }_j\right) + b_i + \epsilon_{ij}$$

Data presentation:

The least squares means will be estimated by visit along with the associated 95% CI. Geometric least squares mean values will be obtained by exponentiating the least squares means.

The treatment effect will be expressed as the % change in ALP for each setanaxib dose versus placebo, derived from the geometric least squares mean ratios estimated at Week 24 (and scheduled timepoints up to Week 24) interacted with each treatment arm. The 95% CI and 1-sided p-value will be presented.

To aid interpretation, corresponding estimated absolute change from baseline for each arm and the estimate absolute change versus placebo and 95% CIs will be estimated from the ratios.

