Note, individual covariate terms for time from treatment discontinuation may be dropped from the model and/or factor levels removed if a particular pattern of missing data is not present when data are unblinded. In particular, if there are subjects present with missing data for a specific level of one of the covariates for time from treatment discontinuation, but there are no matching subjects with data observed for the same level of the same factor in the same treatment arm, the factor level will be grouped with the next highest level to enable the imputation model to be run (for example Week 2 will be grouped with Week 4). This will require running separate MI procedures if the pattern differs by treatment arm.

In the event that the above model fails, the time from treatment discontinuation covariates may be removed as follows

Sponsor: Calliditas Therapeutics Suisse SA

Protocol No: GSN000350

Proc mi data=partial nimpute=1 seed=439384 out=impute minmaxiter=100000; monotone regression; var BASE VAL1-5; by TRT imputation_; run;

Step 3: the MMRM model is applied to the transposed, imputed data. Any subject who dies prior to a visit will have worst case data imputed only at this stage prior to analyzing the data. Baseline ALP will be included as a covariate and will be calculated as the geometric mean of pre-randomization ALP results, as defined in section 10.1 and log-transformed prior to inclusion in the analysis model. The model will also include terms for treatment group, visit, log(baseline) by visit, and visit by treatment group interaction. Subject will be included as a random effect.

An unstructured covariance matrix will be used to model the within-subject correlation of data. The Kenward-Roger's degrees-of-freedom adjustment will be used. Restricted maximum likelihood will be used to obtain parameter estimates. Model assumptions of the MMRM will be assessed using residual plots (such as q-q plots, histograms, box plots, and scatter plots). If the model above does not converge, heterogeneous Toeplitz covariance structure will be used instead of the unstructured covariance matrix. If convergence still does not meet, the Toeplitz structure will be used.

```
proc mixed data=imputed method=reml;
    class TRT USUBJID VISIT;
    model CHG = TRT VISIT BASE BASE*VISIT VISIT*TRT /ddfm=kr;
    repeated VISIT/ sub = USUBJID type = un;
    lsmeans TRT*VISIT /cl pdiff;
    by _imputation_;
    ods output LSMeans=mixlsmean Diffs=mixdiff;
run:
```

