log-transformed data will be analyzed using Robust Regression with independent variables of treatment and log transformed baseline ALP. M-estimation will be used with Huber weights and a cut-off value of 2 with the median method used to estimate the scale parameter. This approach means that standardized residuals with an absolute value of ≤ 2 , corresponding to the central 95% of the data if normally distributed, have equal weight and outlying data are weighted according to a pre-specified function, Wc (x), which gives lower weights to the most outlying data where Wc (x) = min {1, c / |x| } where x is the standardized residual, corresponding to least square standardized residuals in the first iteration. Given that dependent variables are categorical and inclusion criteria for the only continuous covariate, log-transformed baseline ALP, prevents this variable from having outlying values, M-estimation will be appropriate.

In the pooling phase, estimated treatment effects and associated standard errors from each imputation will be combined using Rubin's rules to provide an overall treatment effect, associated 95% CI, and 1-sided p-value.

```
proc mianalyze data=est1;
modeleffects estimate;
stderr stderr;
ods output ParameterEstimates=est2;
run;
```

Version Date: 27-June-2024 Sponsor: Calliditas Therapeutics Suisse SA

Protocol No: GSN000350

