12.5.3 Secondary Estimands

12.5.3.1 Secondary Analyses

The secondary estimands are:

- To assess the change in fatigue (as assessed by the **PROMIS-short form-Fatigue 7b Daily** and by the **PBC40 fatigue domai**n) over 24 weeks in subjects with PBC, elevated liver stiffness, and intolerance or inadequate response to UDCA. The intercurrent events are as defined for the primary estimand (see Table 5).
- To assess the change in liver stiffness over 24 weeks in subjects with PBC, elevated liver stiffness, and intolerance or inadequate response to UDCA. The intercurrent events are as defined for the primary estimand (see Table 5).
- To assess the change in ALP, fatigue and liver stiffness in subjects with PBC, elevated liver stiffness, and intolerance or inadequate response to UDCA, where both setanaxib doses are

Version Date: 27-June-2024

Sponsor: Calliditas Therapeutics Suisse SA

Protocol No: GSN000350

combined into one setanaxib treatment group. The intercurrent events are as defined for the primary estimand (see Table 5).

The primary analysis methodology described in Section 12.5.2.1 will be repeated for the secondary estimands, with the exception that the outcome variable for analyses of fatigue will be absolute change from baseline (*calculated as postbaseline minus baseline values*) with no log transformation and the baseline covariate in the model will not be log transformed. As described below, Y_{ij} is the observed response (absolute change in fatigue at visit i (up to Week 24) to baseline).

$$Y_{ij} = \beta_0 + \beta_1$$
 · Treatment $_i + \beta_2$ · Visit $_j + \beta_3$ · (Baseline fatigue $_{ij}$) + β_4 · (Baseline fatigue $_{ij}$ × Visit $_j$) + β_5 (Treatment $_i$ × Visit $_j$) + b_i + ϵ_{ij}

For the analysis of fatigue, fatigue data captured at Baseline, Weeks 4, 12, and 24 will be included in the model. Subjects enrolled under protocol version 1.0 and reconsented to version 2.0 will have no baseline value for the PROMIS-short form-Fatigue 7b as this questionnaire was introduced in version 2.0 at the request of the FDA. A sensitivity analysis will be performed with imputation of missing data.

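### The SAP's primary MMRM text adds a redundant random subject effect and iid errors to an unstructured covariance, and drops the protocol's ALP stratum; SAP 6.1 flags neither that omission nor the added baseline-by-visit term

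*SAP*

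**What the plan says.** **Protocol 8.4.1.1** models log ALP minus log baseline on log(baseline), the ALP stratum, treatment, visit and treatment-by-visit. The covariance is unstructured, with REML and Kenward-Roger. There is no random subject effect and no baseline-by-visit term. The stratum may leave the model on one condition: too few patients at either level. If the fit fails, the covariance goes to heterogeneous Toeplitz and then Toeplitz, where the sequence stops.

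**SAP 12.5.2.1** has log(baseline), treatment and visit, followed by "log(baseline) by visit, and visit by treatment group interaction. Subject will be included as a random effect". On covariance it says "An unstructured covariance matrix will be used to model the within-subject correlation of data". Under the assessment of model assumptions it says that the residual errors "are assumed to be independent and identically distributed with constant variance". The stratum is absent from the text, from the main equation and from both fallback equations, and the protocol's removal rule is not invoked. After the two Toeplitz structures and some optimiser changes, the fallbacks go on to "removing baseline * visit interaction term and removing the baseline term".

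**SAP 12.5.2.2.1, Step 3** repeats the random-effect wording, but its code reads "repeated VISIT/ sub = USUBJID type = un", with no RANDOM statement and no stratum. This is the only MMRM code in the SAP.

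**Elsewhere in the SAP.** Section 12.5.3.1 says "The primary analysis methodology described in Section 12.5.2.1 will be repeated for the secondary estimands", and its fatigue equation carries a subject effect. Section 6.1 lists two changes from the protocol: the Per Protocol Set definition and the abnormal-laboratory summaries. Protocol 8.1 says that departures from the protocol analysis will be set out in the SAP.

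**The concern.** This model carries the only comparison with type I error control (SAP 12.5.1), so it should be one defined, estimable model before unblinding. Two things look wrong.

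First, the covariance is described in ways that cannot all hold. A programmer who follows the text would add a RANDOM statement; one who follows the Step 3 code would not. If the redundant version is fitted, its covariance parameters are not identified. A convergence or Hessian warning could then move the primary analysis to a fallback it did not need.

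Second, a factor used to randomise, and placed in the model by the protocol, has gone without comment. The SAP has a section for changes from the protocol that is detailed enough to cover laboratory summaries. A reader of 6.1 would conclude that the primary model is unchanged.

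**Working it through.** **Plan's own figures.** SAP 8.1 gives 88.2% power for at least one dose and 68.3% for both. A simulated comparison of means (400,000 trials, 16 per arm, difference 22.5 points, Hochberg, Welch t) gives 88.2% and 68.5% with SD 24 on setanaxib and 19 on placebo. That is the reverse of the order written; the written order gives 84.8% and 71.4%. The SD order is a separate matter. These calculations use no covariate, so the model terms below do not change them.

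**1. Covariance parameters.** There are five post-baseline visits (Weeks 2, 4, 8, 12, 24). An unstructured matrix has 5×6/2 = 15 distinct entries. With a subject effect, V = σ²_b·J + R, where J is all ones and R is unstructured. That is 15 + 1 = 16 parameters mapped to 15 entries, and the Jacobian has rank 15. Any σ²_b that leaves R positive definite gives the same V. On one simulated 66-patient data set the REML log-likelihood was 603.634 at σ²_b = 0, 0.002, 0.005 and 0.01.

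**2. Subject effect plus iid errors.** Here V = σ²_b·J + σ²·I: two parameters, compound symmetry. This is a different model from unstructured.

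**3. Does redundancy alter the answer?** Three simulated trials (48 patients, about 25% monotone dropout, assumed log SD 0.12 rising to 0.24) were fitted both ways. The −2 REML log-likelihoods were −653.58921, −634.71931 and −634.71601 under both. Week 24 contrasts and SEs agreed to 5 decimals. The smallest-to-largest Hessian eigenvalue ratio was 2.7e-5 to 3.0e-5 for unstructured alone, and 3e-9 to 2e-8 (numerically singular) with the intercept. The estimate is unaffected if the fit converges; the weakness is numerical.

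**4. First fallback.** Heterogeneous Toeplitz has 5 variances + 4 correlations = 9 parameters, or 10 with the intercept. With unequal visit SDs the rank is 10 of 10, so the intercept is identified again. It is redundant only if all visit SDs are equal (9 of 10), or under homogeneous Toeplitz (5 of 6).

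**5. Price of restoring the stratum.** Week 24 ANCOVA, 6,000 simulated trials per scenario, 48 patients, effect ln(0.975/0.75) = 0.262, one-sided 0.025. Assumed: Screening ALP lognormal with median 2.6×ULN and log SD 0.4, truncated at 1.67×ULN; within-patient log SD 0.10. Pairwise power (%), by the share of Week 24 variance that baseline explains:

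| Model | 0% | 10% | 20% | 30% |
|---|---|---|---|---|
| Total SD 0.24: log(baseline) | 85.5 | 88.7 | 92.3 | 94.8 |
| Total SD 0.24: plus stratum | 85.2 | 88.3 | 91.8 | 94.5 |
| Residual SD 0.24: log(baseline) | 84.6 | 85.8 | 84.9 | 85.7 |
| Residual SD 0.24: plus stratum | 84.2 | 85.4 | 84.4 | 85.1 |

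The differences are 0.3 to 0.6 points; a repeat simulation gave 0.2 to 0.7. The Monte Carlo SE of each power figure is about 0.5 points. R² between log(baseline) and the stratum was 0.61 to 0.65 over the assumed ALP distributions, so the retained covariate carries much of the same information.

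**The case against.** The strongest reply is that nothing numerical is at stake. The SAP states an unstructured matrix, its code is REPEATED with type=un, and the iid sentence only introduces the residual checks. All three redundant fits reached the same answer, and no failed fit has been shown. The SAP keeps the continuous form of the stratifying variable, and adding the stratum costs a little power rather than gaining any. Protocol 8.1 asks for departures to be set out in the SAP without naming a section, and 12.5.2.1 prints the new model openly. On size, this reply stands. It does not remove the conflicting wording, which Step 3 repeats and which governs an analysis with no code of its own. Nor does it remove the protocol's single condition for dropping the stratum, or the silence of 6.1.

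Stronger readings are tempting but not supported:

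- **Compound symmetry with a wrong Week 24 SE.** If Week 24 were 1.2 times as variable (in SD) as the root-mean-square visit, two-sided error would be about 10%: 2(1 − Φ(1.96/1.2)). But the text names unstructured and the code uses it.
- **Large power loss in the last fallback.** Reaching the model without baseline requires failure of both Toeplitz structures, the optimiser changes and the model without baseline-by-visit. The redundancy normally disappears at the first of these steps. Power figures for that last model should carry no weight.
- **Secondary models and robust regression breach the protocol.** Protocol 8.4.1.5 applies the primary approach only where appropriate, and 8.4.1.3 leaves the robust model to the SAP.
- **Extended fallbacks contradict the protocol.** The protocol is silent on what follows Toeplitz.
- **The stratum was dropped after seeing data.** SAP 6.0 says the blinded team had no access to ALP values.

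**Conclusion.** The point holds as a matter of specification and traceability, and should be fixed. The covariance wording is internally inconsistent: 16 parameters for 15 entries on one reading, compound symmetry on another. Unstructured alone is clearly intended. The randomisation stratum is missing from the primary model without the protocol's condition being invoked. SAP 6.1 records neither that nor the added log(baseline)-by-visit term.

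The effect on the Week 24 estimate is probably small. The redundant intercept changes nothing if the fit converges, and log(baseline) remains in the model. No bias or type I inflation is shown; even with neither baseline nor stratum, 12,000 simulated null trials gave 0.022 and 0.016 against a nominal 0.025 (baseline explaining 10% and 30%). The rank results are exact. Every power, error-rate and Hessian figure rests on assumed log-scale SDs and ALP distributions, because the documents give none.

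**What to change.** - **SAP 12.5.2.1 and Step 3 text:** delete the sentence making subject a random effect, the b term in all three equations, and the iid/constant-variance sentence. State REPEATED VISIT / SUBJECT=USUBJID TYPE=UN, with Weeks 2, 4, 8, 12 and 24 as responses and baseline only as a covariate.
- **SAP 12.5.3.1:** delete b from the fatigue equation, and from the liver stiffness equation if it is there (the end of that equation is not legible in the text reviewed).
- **Stratum:** add the randomised ALP stratum as a fixed effect to the three primary equations and the Step 3 code, keeping the protocol's removal rule. If the sponsor prefers to leave it out, a justified line in 6.1 closes the record.
- **SAP 6.1:** list the log(baseline)-by-visit term and, for completeness, the fallbacks beyond Toeplitz.
- **Optional:** the stratum in the secondary models and in the robust regression, where the SAP now has "log-transformed data will be analyzed using Robust Regression with independent variables of treatment and log transformed baseline ALP".

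The cost is SAP wording, one model term and one degree of freedom: roughly half a point of power under the assumed SDs. No change to sample size or data collection is needed.

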#### 8.3 Sample Size

The primary efficacy endpoint is the change in ALP (%) over 24 weeks.

It is planned to enroll approximately 60 to 70 patients. Patients will be randomized and allocated to placebo, setanaxib 1200 mg/day, or setanaxib 1600 mg/day according to a 1:1:1 randomization ratio.

This study is designed to detect a >25% reduction in ALP in setanaxib-treated patients versus a 2.5% reduction in the placebo arm with an overall 2-sided p<0.05. Standard deviations are assumed to be 19% and 24%, respectively, based on the Phase 2a study with setanaxib and the Phase 3 POISE study with Ocaliva. With approximately 16 evaluable patients per arm (48 patients overall) and using a Hochberg step-up test to control alpha across 2 dose comparisons versus placebo, this study has 88.2% global power to detect at least 1 treatment arm as significantly different from placebo and 68.3% power to detect both treatment arms as statistically significant. Also, for the secondary endpoint of change in fatigue, there will be >80% power to detect a 20% reduction in fatigue versus a 2.5% increase in the placebo arm.

An assumed dropout rate of approximately 25% leads to a target sample size of 66 enrolled patients (22 per arm). A range of approximately 60 to 70 enrolled patients allows for variability in the assumed dropout rate.

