#### 8.4.1.1 Primary Endpoint Analysis

The primary endpoint is listed in Section 2.1.

For the primary efficacy analysis, each setanaxib treatment group (1600 mg and 1200 mg) will be compared with placebo. The primary estimand is to assess the change in ALP (%) over 24 weeks in patients with PBC, elevated liver stiffness, and intolerance or inadequate response to UDCA.

The following intercurrent events will be considered and further detailed in the SAP. Patients who start additional PBC-related medication(s) after Randomization will have their IMP discontinued (Section 6.7). These patients will be included in the analysis, but efficacy data collected after the start of the new therapy will be excluded. PBC-related medication(s) will be identified through blinded medical review prior to database lock. For all other patients who discontinue from treatment prior to Week 24 but return for the Week 24 Visit (Visit 8), the Week 24 result will be used regardless of the occurrence of the intercurrent event. Patients with missing results will have their values imputed based on observed data. Further details will be defined in the SAP.

The primary endpoint will be evaluated using a mixed model for repeated measures (MMRM) with log(ALP) - log(Baseline) as response with log(Baseline) as a continuous covariate, ALP stratification (<3.0×ULN or ≥3.0×ULN), treatment and visit as categorical covariates and treatment by visit as interaction term. All ALP data captured at Weeks 2, 4, 8, 12, and 24 will be included in the model. The relative mean change from Baseline at Week 24 will be estimated and corresponding 2-sided 95% confidence intervals will be calculated. The relative mean change and confidence intervals will be calculated. The relative mean change and confidence interval will also be converted to the percentage scale, for presentation purposes.

An unstructured covariance matrix will be used to model the within-patient correlation of data. The Kenward-Roger's degrees-of-freedom adjustment will be used. Restricted maximum likelihood will be used to obtain parameter estimates. The least squares means will be estimated by visit along with the associated 95% confidence intervals and p-values with the analysis taken from the estimate at 24 weeks. In the case of insufficient patients at either level of the stratification, the stratification factor will be removed from the model.

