Model assumptions of the MMRM will be assessed using residual plots (such as q-q plots, histograms, box plots, and scatter plots). If the model above does not converge, heterogeneous Toeplitz covariance structure will be used instead of the unstructured covariance matrix. If convergence still does not meet, the Toeplitz structure then will be used.

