## 8.4.1.2 Multiplicity

The null hypothesis is no difference in change in ALP (%) between setanaxib and placebo over 24 weeks. The alternative hypothesis is that setanaxib demonstrates a difference in change in ALP (%) over placebo.

In order to control the study-wise error rate, that is, the probability of rejecting the true null hypothesis for the primary endpoint at 1-sided 0.025, a Hochberg step-up procedure will be applied to adjust for 2 dose comparisons versus placebo.

For the analysis of secondary and exploratory endpoints, "nominal" p-values will be presented and will not be considered as part of the study-wise control of type I error. This is considered appropriate for an exploratory Phase 2b study.

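### The last step of the SAP's convergence ladder drops log(baseline) from the primary MMRM, an undeclared departure from the protocol that is unlikely to cure non-convergence and would cost some precision

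*SAP*

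**What the plan says.** **Protocol 8.4.1.1.** The response is the log ratio of ALP to baseline. The model has "log(Baseline) as a continuous covariate", the ALP stratum, treatment, visit and treatment by visit. If it does not converge, only the covariance changes: unstructured, then heterogeneous Toeplitz, and finally "If convergence still does not meet, the Toeplitz structure then will be used". The one term the protocol allows to be dropped is the stratification factor, and only for sparse strata.

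**SAP 12.5.2.1.** The model has treatment, visit, log(baseline), log(baseline) by visit and treatment by visit. The ALP stratum is absent. An unstructured matrix is specified, and in addition "Subject will be included as a random effect". The ladder follows the protocol as far as Toeplitz, then considers optimiser changes, and then reduces the mean model by "removing baseline * visit interaction term and removing the baseline term". Two formulas are printed. The first drops only the interaction. The second contains treatment, visit, treatment by visit and the subject effect, with no baseline. The text does not say which covariance structure goes with the reduced models.

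**SAP 12.5.2.2.1, Step 3 (sensitivity analysis #1).** The same model is described, but the ladder stops at Toeplitz and baseline stays. The sample code has a REPEATED statement with an unstructured matrix and no RANDOM statement.

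**SAP 6.1.** Two changes from protocol are listed, the per-protocol set definition and the laboratory summaries. Neither concerns the primary model.

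**SAP 12.5.3.1.** The primary methodology is repeated for the secondary estimands, so the same fallback could apply to fatigue and liver stiffness.

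**The concern.** A convergence ladder should simplify the part of the model that is failing. In an MMRM that is usually the covariance, with 15 unstructured parameters for five visits. Baseline is a single, fully observed covariate. It is there for precision and to correct chance imbalance, and taking it out leaves the covariance problem where it was.

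If the last model were used, the primary comparison would carry no ALP covariate of any kind, although randomization is stratified on Screening ALP. It would be an analysis the protocol does not describe. It could also differ from sensitivity analysis #1 in its covariates as well as in its missing-data handling, so a difference between the two would be hard to interpret.

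**Working it through.** **1. The plan's own power figure.** Inputs from protocol 8.3 and 8.4.1.2: a 25% versus 2.5% reduction (difference 22.5 points); "Standard deviations are assumed to be 19% and 24%, respectively"; 16 evaluable patients per arm; error controlled "at 1-sided 0.025, a Hochberg step-up procedure will be applied to adjust for 2 dose comparisons versus placebo". Simulating Hochberg with these inputs gives 87.8% to 87.9% power for at least one dose (three-arm pooled t, or z), against the stated 88.2%, so that figure reproduces. Power for both doses comes to 72% to 76% with the SDs in the stated order. The stated 68.3% is approached (69.1%) only with the SDs swapped, which is a separate matter. Pairwise two-sample t power is 81%.

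**2. Precision cost of dropping baseline.** Let r be the within-arm correlation between log(baseline) and the log ratio. Adjustment multiplies the residual variance by (1 − r²), so dropping baseline multiplies the standard error by 1/√(1 − r²). This ignores the one degree of freedom the covariate uses, a small offset the other way. The documents give no r; the range is assumed.

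| r | variance ratio 1/(1 − r²) | rise in SE |
|---|---|---|
| 0.1 | 1.010 | 0.5% |
| 0.2 | 1.042 | 2.1% |
| 0.3 | 1.099 | 4.8% |
| 0.4 | 1.190 | 9.1% |
| 0.5 | 1.333 | 15.5% |

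If log ALP has equal variance at baseline and Week 24 with correlation ρ, then |r| = √((1 − ρ)/2). So ρ = 0.9 gives 0.22, ρ = 0.8 gives 0.32, and r = 0.5 needs ρ as low as 0.5.

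**3. What this means for power.** The documents do not say whether the 19% and 24% SDs are baseline-adjusted, so both readings are shown (Hochberg, at least one dose, Welch tests, simulated):

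| r | SDs already adjusted: power after dropping baseline (84.7% with it) | SDs unadjusted: power with baseline kept (84.5% without it) |
|---|---|---|
| 0.2 | 83.3% | 86.0% |
| 0.3 | 81.3% | 88.0% |
| 0.4 | 77.7% | 90.3% |
| 0.5 | 73.3% | 93.5% |

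**4. Does removing baseline help convergence?** REML fits to simulated five-visit trials (22 per arm, 25% monotone dropout) compared three mean models: with baseline by visit, with baseline only, and without baseline. The measure was the ratio of smallest to largest eigenvalue of the Hessian for the covariance parameters.

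- Unstructured: 0.0025 to 0.004 for all three mean models.
- Unstructured plus a random subject intercept, as the SAP formula is written: of the order of 1e-8 or less for all three.

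Removing baseline did not improve conditioning. Adding the random intercept destroyed it. In six of these trials (r = 0.3) the mean Week 24 SE was 0.066 with baseline by visit and 0.071 without baseline, about 6% to 7% larger. That agrees roughly with step 2, on few replicates.

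**5. Is the random subject effect identifiable?** It adds the same constant to every element of the covariance matrix.

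- Unstructured: the matrix absorbs the constant, so the effect is redundant.
- Homogeneous Toeplitz: also redundant (6 parameters, rank 5).
- Heterogeneous Toeplitz with unequal visit variances: identifiable, though weakly (10 parameters, rank 10). Rank falls to 9 when the variances are equal.

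**The case against.** The best defence is that the step is remote. Three covariance structures must fail, then the optimiser changes, then the model that drops only baseline by visit. That stands, and it is why severity is low.

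A reader might infer that the step is likely, because the random subject effect is not identifiable alongside an unstructured matrix and the ladder would therefore run to its end. The documents do not support this. A redundant parameter leaves a flat ridge in the likelihood, which is not the same as failure to converge. In four of four simulated trials the unstructured model with a random intercept still converged, to the same REML likelihood as without it (own optimiser, not SAS). The SAP's first fallback, heterogeneous Toeplitz, is identifiable when visit variances differ. The SAP's sample code for sensitivity analysis #1 omits the random effect, so the phrase may be loose wording.

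A reader might also infer a definite power loss, for example pairwise power falling from 81% to 77% (r = 0.3) or 69% (r = 0.5). Those figures require the planning SDs to be baseline-adjusted already, which neither document states, and an r that neither gives. If the SDs are unadjusted, the baseline-free model still has the 81%.

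It is also fair that the outcome is already a ratio to each patient's own baseline and that randomization is stratified on Screening ALP. Both limit the harm from chance imbalance. Neither is a reason to prefer the baseline-free model.

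**Conclusion.** The point holds at low severity. The SAP prints a last-resort primary model without baseline, which the protocol does not provide for, SAP 6.1 does not declare, and the SAP's own sensitivity ladder does not share. Removing the term is unlikely to cure non-convergence; to say that it never could would be too strong.

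If the step were reached, the contrast would remain unbiased under randomization, with a standard error about 2% (r = 0.2), 5% (r = 0.3) or 15% (r = 0.5) larger. The cost would be nil if baseline were unrelated to change. These sizes rest entirely on the assumed r.

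Dropping only baseline by visit is acceptable, since the protocol model has no such term. The random subject effect on top of an unstructured matrix is a separate wording fault: it is redundant and disagrees with the SAP's sample code.

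**What to change.** In SAP 12.5.2.1:

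- Delete the second reduced formula and the reference to removing the baseline term.
- State that log(baseline) stays in every fallback. The model without baseline by visit may remain.
- Remove the random subject effect wherever a REPEATED covariance is used, here and in Step 3 of 12.5.2.2.1, so that text and code agree.
- End the ladder with a simpler covariance, such as compound symmetry or AR(1), retaining Kenward-Roger, and say which structure accompanies each reduced model.
- Restore the protocol's ALP stratum or declare its omission in 6.1, along with any other remaining difference from the protocol model.

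Two alternatives are less attractive as the last step. Empirical standard errors tend to be too small at about 16 patients per arm and would displace Kenward-Roger. A Week 24 ANCOVA would leave out patients without Week 24 data when about 25% dropout is assumed, and so would change the missing-data handling of the primary test.

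The cost is SAP wording only, before database lock. No new data or patients are needed.
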